Södra Älvborgs Hospital, Borås, Sweden

e-mail: [contact]

[name]

Frölunda sjukhus, Västra Frölunda, Sweden

e-mail: [contact]

Summary

Background

Stress related ill health is today a common cause for long term sick leave among women in their midst of life as well as being a common cause for visits to the primary health care.

Aim

To investigate the effect on mental health, quality of life and sick leave of education provided within the primary health care given in group or individually for women aged 45-60 years with stress related symptoms.

Methods

This is a randomised controlled clinical trial using a two factor design.

Education is given as four sessions exploring menopause, physiology, oestrogen deficiency, cardiovascular health, consequences of stress, mental health, relationships, sexuality and lust as well as potential actions to improve the situation. In addition, the group sessions will touch base on topics like obstacles and resources, coping strategies, and behavioural changes.

The individual education will be person-centred and given as five sessions focusing on stress related symptoms, ill health, physiology and coping strategies.

Expected result

If any of these two interventions turns out to be successful it may provide low cost intervention options for a common problem often seen in primary health care.

Study protocol: Effect of primary care education on mental health, quality of life, need for sick leave and health care consumption in women 45-60 years with stress-related symptoms. A randomized controlled trial.

Introduction

Stress-related ill health is today the most common cause of long-term sick leave in women in the middle of life and a common cause of primary care visits (1). It is clear that women suffer from long-term sickness and ill health to a greater degree than men (2). Women's physical and mental health in Sweden shows a marked decrease in the ages of 45-60 years (3). During this life phase, called menopause, the woman undergoes a hormonal transformation (3). Stress-related symptoms appear after a long time with high stress load without sufficient recovery (4). There are currently few studies with high evidence-based treatment on stress-related symptoms (5). Busch et al show in an evaluation that 70% of people who have undergone rehabilitation overall are satisfied with the treatment. The treatment, on the other hand, has not led to increased return to work (6).

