23. What is the effect of Structured person-centered support (PCS) on visits to primary health care (women are asked at baseline if they had to visit the primary health care center during the preceding two months. The same question is asked at 6 months. The measurement is the change in proportion of women who visited the primary health care center)?
24. What is the effect of Structured person-centered support (PCS) on visits to primary health care (women are asked at baseline if they had to visit the primary health care center during the preceding two months. The same question is asked at 12 months. The measurement is the change in proportion of women who visited the primary health care center)?

Methods

Selection of patients, inclusion criteria and logistics

Women, 45-60 years old, reached through advertisements in newspapers and on a website, are offered to participate in the study. Application for participation in the study is made electronically via Fou Primary Care Södra Älvborg website or by telephone to research nurse. Inclusion criteria:

Study protocol: Effect of primary care education on mental health, quality of life, need for sick leave and health care consumption in women 45-60 years with stress-related symptoms. A randomized controlled trial.

- a. The woman has some mental and / or physical health problems such as depression, anxiety, gastrointestinal symptoms, muscular symptoms and / or cardiovascular symptoms.
- b. The woman has been on sick leave for a maximum of 30 days in the last two months.
- c. The woman has no major language difficulties that prevent understanding and speaking Swedish language as well as filling in forms.
- d. Woman lacks serious illness such as psychosis, severe depression or dementia
- e. The woman is not treated in palliative care
- f. The woman has no ongoing drug or alcohol abuse.

Research nurse contacts the woman via telephone and provides further information about the study where the opportunity is given to ask questions. If the woman meets all inclusion criteria and choose to accept the study, electronically self-administered questionnaires about self-assessed health and health-related quality of life will be sent to all participants, as well as a written informed consent that is signed. Self-administered questionnaires and consent kits are filled in via link on R & D Primary Care Södra Älvborg's website.

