The research nurse is responsible for administration of questionnaires and arranging physical check-up.

Group allocation

Research randomizer is used to generate a random series based on block-randomization in blocks of four. The random series is transferred to closed sealed opaque envelopes, each containing group assignment. The manufacture of these closed envelopes is done by a person who is not involved in the study.

Randomization occurs after the woman answered all questionnaires at baseline. Then the research nurse opens the next sealed numbered envelope and the patch inside describes what group the woman is allocated to:

- Group 1: group information (GI)
- Group 2: group information (GI) + person-centred support (PCS)
- Group 3: person-centred support (PCS)
- Group 4: no GI or PCS (control group)

Intervention

Group information (GI).

Midwives and district nurses participate as group leaders. Each group training includes 12 women and comprises four one-and-a-half hours of information with topics related to physical and mental changes in the body as well as conversations aimed to make behaviour, consequences of behaviour and choices in life conscious.

Study protocol: Effect of primary care education on mental health, quality of life, need for sick leave and health care consumption in women 45-60 years with stress-related symptoms. A randomized controlled trial.

The first group event contains education with the definition and myths of "middle of life" / menopause, physiology, menstrual cycle, hormonal conversion, local oestrogen deficiency symptoms, osteoporosis and information on treatment options and self-care advice.

The second group event contains teaching and information on cardiovascular health, its risk and health factors, physiology, mental health, relationships, sexuality and lust as well as information on treatment options and self-care advice.

The third group event contains insights into stress-related ill health, physiology, social relationships in family and work, sexuality and lust, insight into obstacles and resources, coping strategies and behavioural changes to promote health.

The fourth group event contains insights on relationships, sexuality and lust as well as a summary of "How do we want to live to feel good?" Insight into obstacles and resources, coping strategies and behavioural changes to promote health.

Structured person-centred support (PCS):

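### One fixed block size of four over four groups makes allocation partly predictable to the research nurse who telephones candidates and opens the envelopes

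*Combined protocol and SAP*

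**What the plan says.** Under Methods, Group allocation, the protocol says: "Research randomizer is used to generate a random series based on block-randomization in blocks of four". It lists four groups: GI, GI plus person-centred support (PCS), PCS, and control. It gives no allocation ratio, no stratification, no variation in block size and no instruction to keep the block size from study staff.

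Three safeguards are stated. The envelopes are sealed, opaque and numbered. They are made by a person outside the study. They are opened only after the woman has answered the baseline questionnaires. On the opening itself the text reads: "Then the research nurse opens the next sealed numbered envelope and the patch inside describes what group the woman is allocated to".

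Under Selection of patients, inclusion criteria and logistics, the same role speaks to candidates before entry: "Research nurse contacts the woman via telephone and provides further information about the study where the opportunity is given to ask questions". Consent and questionnaires follow "If the woman meets all inclusion criteria and choose to accept the study". No separate eligibility assessor is named. Under Data collection, the research nurse also gathers the data at baseline and at both follow-ups.

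**The concern.** Opaque envelopes stop anyone from reading the next allocation. They do not stop someone who has opened the earlier ones from deducing it. With four groups and blocks of exactly four, three opened envelopes determine the fourth. The person who sees that sequence is also the person who talks to candidates, and the first inclusion criterion (some mental or physical health problem) leaves room for judgement.

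Concealment matters more here than in many trials. Women know whether they attend sessions, and every outcome in the research questions is self-reported. The planned regression adjusts only for age besides the two interventions and their interaction. If knowledge of the next allocation influenced who was encouraged to join, or which of several ready women was randomised next, the resulting difference in severity or motivation would enter the GI and PCS contrasts uncorrected.

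**Working it through.** The plan gives no figure for predictability, so there is none to reproduce.

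**Inputs.** Block size 4, four groups, and envelopes opened in sequence by the research nurse (Group allocation); 370 women planned (Sample size estimation). Assumption: 1:1:1:1 allocation, so each group occurs once per block. The observer is assumed to know the block size and all earlier allocations.

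**Does the nurse need to be told the block size?** No. Without blocking, four successive allocations would all differ with probability 4!/4^4 = 24/256 = 9.4%. Three such runs in succession would have probability 0.094^3 = 0.08%. The pattern shows itself after a few blocks.

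**Arm, at the moment of opening.** The chance that the best guess is right, by position in the block, is 1/4, 1/3, 1/2, 1. The mean is (0.250 + 0.333 + 0.500 + 1.000)/4 = 52%, against 25% by chance. Only the fourth position is certain. 370 = 92 × 4 + 2, so there are 92 complete blocks and 92 certain allocations (25%).

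**GI yes or no, the factor in the primary question.** Each block holds two GI and two non-GI places. Best-guess accuracy by position is 1/2, 2/3, 2/3, 1, with mean 71% against 50% by chance. The fourth position is always certain. The third is certain when the first two have the same GI status, which has probability 1/3. The certain share is (1 + 1/3)/4 = 1/3. Over 92 blocks this is 92 × 4/3 = 122.7, about 123 women.

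**At the telephone call.** Let m be the number of other women randomised between a woman's call and her own envelope. Enumerating the 24 block orders gives:

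| m | Arm: guess right | Arm: certain | GI: guess right | GI: certain |
|---|---|---|---|---|
| 0 | 52% | 25% | 71% | 33% |
| 1 | 33% | 0% | 58% | 8% |
| 2 | 27% | 0% | 54% | 0% |
| 3 or more | 25% | 0% | 50% | 0% |

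The documents do not give m, so the whole range is possible.

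**Effect of mixed block sizes.** Lists of 370 were simulated with sizes 4, 8 and 12 in random order. The observer knows the set of sizes but not their order, and updates on every opened envelope.

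| Scheme | Arm: certain | Arm: guess right | GI: certain | GI: guess right |
|---|---|---|---|---|
| Fixed 4 | 25% | 52% | 33% | 71% |
| Random 4, 8, 12 | 3.6% | 46% | 5% | 66% |

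In women, certain arm predictions fall from 92 to about 0.036 × 370 = 13, and certain GI predictions from about 123 to about 0.05 × 370 = 19.

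**The case against.** The strongest reply is that the plan already has real safeguards. Independent preparation and sealed, opaque, numbered envelopes mean that the list cannot be read ahead. This stands. A reader might infer that concealment fails outright, and the documents do not support that: nothing is known at the first place of a block, the arm can only be guessed with limited success at the second and third, and it is certain only at the fourth.

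Timing also counts. Eligibility and encouragement belong to the call. Consent and questionnaires are then completed electronically, and only afterwards is the envelope opened. If even one other woman is randomised in between, no arm is certain at the call; after three, prediction is no better than chance. Recruitment through newspaper and website advertisements makes overlap plausible, though the documents do not state it. So the headline percentages are upper limits for this route.

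The nurse's discretion is partly inferred. The text does not say that the nurse decides eligibility or chooses the order among women who are ready. It names no other assessor and fixes no order, so the route is open rather than documented. Both interventions are delivered by midwives and district nurses, and no motive for the research nurse to steer is described. A reader might go further and conclude that the GI and PCS contrasts are no longer randomised comparisons. That would require steering to have taken place, and nothing in the documents shows it.

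Finally, mixed block sizes do not make allocation unpredictable. Some allocations stay certain, and the guessing advantage shrinks only modestly. That is a fair limit on the remedy, but it does not remove the reason for it.

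**Conclusion.** The point holds as partial predictability. Assuming equal allocation within blocks, the research nurse can deduce the arm for 92 of 370 women and GI status for about 123 of 370 when the envelope is opened, with best-guess accuracy of 52% and 71%. At the telephone call, predictability lies between those values and chance, depending on how many women are randomised in between. Influence on entry or on the order of randomisation is a possibility that the design leaves open, and its size cannot be estimated from the documents. The arithmetic is secure; the step from predictability to bias is not established. The change is worth making because it costs little and removes most of the certain predictions.

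**What to change.** In Group allocation, replace the single block size by sizes of 4, 8 and 12 in random order. The uninvolved person who makes the envelopes should generate the list, and the sizes should be kept out of any document that the research nurse uses. State the allocation ratio. Add that envelopes are opened strictly in the order in which women complete the baseline questionnaires; this closes the reordering route, which changing the block sizes does not.

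The cost is one new random list and a few sentences. Final arm sizes may differ by up to about three women, because an unfinished block of 12 holds at most three places per arm; in 370 women this is negligible.

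If existing staffing allows, the envelopes should be held and opened by someone without contact with candidates. That would remove most of the remaining route, including the guessing advantage that mixed block sizes leave in place.

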Research shows that women often lack information about physical and mental and urogenital changes under the "middle of life" / menopause (7).

Group education is a method and participation in group education can be a good way for women to get information and exchange experiences (8).

Earlier studies evaluating patient education in hypertension and diabetes show significant improvement (9.10). Talking can raise awareness about choices and consequences, create insight into behaviours and provide insight into the overall life situation to find the core of ill health (11). Arving et al shows that health-related quality of life increased faster in patients receiving support calls than those who received normal treatment (12).

There is a lack of primary care studies that evaluate the effect of education in group and / or individually for women 45-60 years with stress-related symptoms.

The vast number of middle aged women with ill health and subsequent high risk for disease risk and increasing number of long-term sick leave shows that it is important to study women's health in this age group.

Aim

To study the effect of education in a group or individually delivered in primary health care on mental health, quality of life and sick leave in women aged 45-60 with stress-related symptoms.

Research questions

- A. Is there any effect of group information (GI) on quality of life, mental health, sick leave or visits to a primary health care centre compared to a control group?
 1. What is the effect of group education (GI) on quality of life (measured by change in scores in SF36 from baseline to 6 months after completed intervention) –
Primary research question (other questions are secondary).

Study protocol: Effect of primary care education on mental health, quality of life, need for sick leave and health care consumption in women 45-60 years with stress-related symptoms. A randomized controlled trial.

2. What is the effect of group education (GI) on quality of life (measured by change in scores in SF36 from baseline to 12 months after completed intervention)
3. What is the effect of group education (GI) on change in number of days on sick leave. (At baseline the number of days on sick leave up until present time is stated by women currently being on sick leave. At the 6 month follow the same information is retrieved is retrieved. The change is the difference between these measurements.)

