Data is collected by the research nurse at baseline and six and twelve months after completion of education. Returned questionnaires are encoded and code lists will be filed at the R & D unit Södra Älvborg in a locked and fireproof archive for more than ten years. Code key is stored separately. Access to the material has project managers and supervisors. Electronic stored data is stored on the computer's network device H so it is backed up automatically, not on the workstation hard drive. Data is stored on the Västra Götaland region password-protected computer. Tape and video recordings are not used.

Study protocol: Effect of primary care education on mental health, quality of life, need for sick leave and health care consumption in women 45-60 years with stress-related symptoms. A randomized controlled trial.

Statistical analysis

Questionnaires are summarized according to manuals. Data is described descriptively with appropriate estimates. The scientific research questions will be analysed by multivariate regression where the two interventions GI and PCS, each being an independent variable, is entered a two-factor model, where interaction effects between the two interventions is also evaluated. Moreover, age becomes an independent confounding variable. A regression is made for each outcome measure (each scientific question). The level of significance is set to ≤ 0.05 . IBM SPSS version 20 or later will be used.

Sample size estimation

Sample size estimations are made for research questions 1, 3 and 5. When estimating sample size, we assume a significance level of 0.05, power of 0.80 and that we do a two-way test. When estimating sample sizes, we use simple group comparison for two independent groups with Mann-Whitney's test as surrogate test.

Research question	Assumptions	Assumed "Effect size"	Number required
1 (primary)	We assume that the quality of life increases by three points in the intervention group and zero points in the control group. Furthermore, the standard deviation is eight in both groups.	0,38	236
3	We assume that days on sick leave decrease by two days in the intervention group and by 0.5 days in the control group. Furthermore, the standard deviation is five days in both groups.	0.30	368

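### GI is taught in groups of 12, but the regression and sample size treat all women as independent; if the sessions themselves make outcomes correlate, the GI standard error is too small, by an amount the documents cannot fix.

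*Combined protocol and SAP*

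**What the plan says.** All references are to the combined protocol and SAP.

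- **Group allocation:** the random series is "based on block-randomization in blocks of four", and one envelope is opened per woman. Groups 1 and 2 receive GI; Groups 3 and 4 do not.
- **Intervention, Group information (GI):** "Midwives and district nurses participate as group leaders". On size and format, "Each group training includes 12 women and comprises four one-and-a-half hours of information". The content includes "conversations aimed to make behaviour, consequences of behaviour and choices in life conscious".
- **Research questions:** question 1, the effect of GI on SF-36 change at 6 months, is marked "Primary research question (other questions are secondary").
- **Statistical analysis:** one regression per outcome, "where the two interventions GI and PCS, each being an independent variable, is entered a two-factor model", with their interaction and age. No education-group term, clustered standard error or random effect is mentioned.
- **Sample size estimation:** "we use simple group comparison for two independent groups", with the Mann-Whitney test as surrogate. No ICC or design effect is given. The totals are 236, 368 and 312 for questions 1, 3 and 5, and 370 women are planned.

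The document does not say how education groups are formed, whether Groups 1 and 2 attend the same sessions, or how the GI factor is coded.

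**The concern.** Twelve women who share a leader and the same conversations may end up with more similar outcomes than twelve unrelated women. This grouping exists only among women who receive GI, so the design is partially nested. Ordinary regression counts each GI recipient as a full independent observation. If the sessions induce correlation, the standard error of the GI effect is too small, its 95% interval too narrow and its p-value too low. The primary question is a GI question, so it is exposed.

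The source of the correlation matters. Similarity that comes only from who is grouped together, such as women recruited in the same period, is shared by all arms because randomisation is in small blocks, and it does not inflate the GI test. Excess type I error needs group effects that vary around a zero average.

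**Working it through.** **Step 1. Reproduce the plan's totals.** Inputs from the sample size table: two-sided 0.05, power 0.80, and d = 3/8 = 0.375 (question 1), 1.5/5 = 0.300 (question 3), 1.6/√((5.0² + 4.8²)/2) = 0.326 (question 5). Noncentral-t power with the Mann-Whitney efficiency 3/π gives 236, 368 and 312, exactly as printed. These totals therefore contain no allowance for clustering.

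**Step 2. Variance of the pooled GI contrast.** Inputs: group size m = 12 (plan); about half of 370 women, 185, receive GI (four arms in blocks of four, taken as equal allocation); 185/12 ≈ 15 groups. The ICC is assumed. Also assumed: full groups, equal total variance with and without GI, no dropout.

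- Design effect in the GI half: DE = 1 + 11 × ICC.
- Variance ratio to the independence assumption: r = (DE + 1)/2.
- True error of the nominal 5% test: 2 × (1 − Φ(1.96/√r)).

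| Assumed ICC | r | True error, pooled GI main effect | Coverage of nominal 95% interval |
|---|---|---|---|
| 0.01 | 1.055 | 5.6% | 94.4% |
| 0.02 | 1.110 | 6.3% | 93.7% |
| 0.05 | 1.275 | 8.3% | 91.7% |
| 0.10 | 1.550 | 11.5% | 88.5% |

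**Step 3. Other contrasts and group sizes.**

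- *Group 1 v Group 4, sessions shared.* About 6 women of each arm per session, so DE = 1 + 5 × ICC and r = 1.025, 1.05, 1.125, 1.25. The error is 5.3%, 5.6%, 6.5% and 8.0% at the same four ICCs.
- *Eight analysed women per group, pooled contrast.* DE = 1 + 7 × ICC, so r = 1.175 and 1.35 at ICC 0.05 and 0.10. The error is 7.1% and 9.2%.
- *Sessions separate by arm.* Group 1 v Group 4 then has DE = 1 + 11 × ICC. Simulated errors at ICC 0.05 are about 8% for Group 1 v Group 4, 8.5% for the PCS main effect and 8.2% for the interaction. With shared sessions, the PCS and interaction tests stayed near 5%.

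**Step 4. Simulate the planned regression** (370 women, blocks of four, shared sessions filled in recruitment order, 20,000 runs, mean GI effect zero).

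| Source of correlation | ICC | Planned GI test | Clustered test |
|---|---|---|---|
| None | 0 | 5.0% | 5.3% |
| Sessions | 0.05 | 8.4% | 5.1% |
| Sessions | 0.10 | 11.4% | 5.0% |
| Recruitment period | 0.05 | 4.3% | 2.5% |
| Recruitment period | 0.10 | 4.0% | 1.3% |

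The clustered test is the same regression with standard errors clustered by education group, a K/(K−1) correction and Satterthwaite-type degrees of freedom.

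**Step 5. Power at 370, pooled contrast,** on the Step 1 basis with variance multiplied by r.

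| Question | ICC 0 | ICC 0.05 | ICC 0.10 | ICC where power reaches 0.80 |
|---|---|---|---|---|
| 1 (primary) | 0.94 | 0.875 | 0.81 | 0.104 |
| 3 | 0.80 | 0.70 | 0.62 | 0.001 |
| 5 | 0.86 | 0.77 | 0.69 | 0.035 |

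Question 3 has almost no reserve in any case: 370 planned against 368 required.

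**The case against.** The strongest objection is that the harm is conditional and its size cannot be read from the documents. There is no ICC; at 0.01 the excess is under one percentage point; and if GI changed no woman's outcome, randomisation would protect the test. All of this stands. What it does not touch is the interval: when group effects vary, the stated precision of the GI estimate is too high whatever the average effect.

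Second, the pooled figures are the high end. The research questions compare GI with a control group. With an interaction term and 0/1 coding, the GI coefficient is Group 1 v Group 4, which is less affected if sessions are shared; dropout also shrinks the groups. This stands, and is why both sets of figures are given. It does not settle the matter, because separate sessions bring that contrast back to about 8% at ICC 0.05.

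Third, a reader might infer two stronger things that the documents do not support. One is that education group will go unrecorded because it is missing from the Data collection list. That list covers baseline, before randomisation, so education group could not be on it. The other is that the protocol itself predicts within-group correlation, because the Introduction says "participation in group education can be a good way for women to get information and exchange experiences". That is general background with a citation, not a description of these sessions. Support for interaction within sessions rests on the conversations in the GI description, which makes correlation plausible but does not establish it.

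Fourth, correcting for groups when the correlation comes only from recruitment period makes the test conservative. This stands as a cost of the fix.

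**Conclusion.** The omission is certain and its size is not. The plan teaches individually randomised women in groups of 12 and analyses them as independent, and no section corrects for this. If the sessions create correlation, the GI standard error is too small, including for the primary question. The true error of the nominal 5% test would be 5.6% to 11.5% (pooled GI main effect, full groups of 12) or about 5.3% to 8.0% (Group 1 v Group 4, shared sessions) over assumed ICCs of 0.01 to 0.10. The effect on the actual result may be negligible.

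It would be wrong to conclude that the primary comparison is underpowered on this account: at 370 women its power stays at about 0.80 or more up to an ICC of about 0.10. Questions 3 and 5 drop below 0.80 at smaller ICCs, but both are secondary. The point should be fixed because the remedy is cheap and because, without group membership, the trial could not show that the ICC is small. Confidence is medium.

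**What to change.** 1. Record an education-group ID for every woman in Groups 1 and 2. State how education groups are formed and whether the two arms share sessions.
2. For continuous outcomes, keep the planned regression but use standard errors clustered by education group, with women who receive no GI as singletons. Use a small-sample correction and Satterthwaite-type degrees of freedom, since there are only about 15 groups. Report the unclustered regression as a sensitivity analysis. Apply this to the GI questions and, if sessions are separate by arm, to the PCS and interaction tests as well.
3. Use the clustered equivalent for the binary visit outcomes.
4. If leaders run several groups, record the leader and add a sensitivity analysis by leader.
5. State the power at 370 over an assumed ICC range, without enrolling more women.

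**Cost:** one or two data fields and SAP wording, somewhat wider intervals and a slightly lower stated power. If the correlation really comes from recruitment period, the clustered test is conservative (2.5% and 1.3% at ICC 0.05 and 0.10 in the simulation), which is the reason to show the unclustered regression beside it.
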